2.5. Interim analyses and stopping guidance

2.5.1. Statistical interim analyses and stopping guidance

The study had a Data Safety Monitoring Board. The members of the DSMB are not involved with the trial in any other way and have no competing interests. The members of the DSMB and the study coordinator will meet annually. The task and responsibility of the DSMB is to do an interim safety analysis when the trial participants have contributed 72 access-related serious adverse events (which is expected at 144 patient-years of follow-up time).

2.5.2. Planned adjustments

This interim analysis is for safety only (i.e. vascular access thrombosis rate, access-related serious adverse event rate and mortality) and not for early stopping for efficacy.

2.5.3. Guidelines for stopping the trial early

The number of vascular access thrombosis and access-related serious adverse events per person-year will be analysed using general linear models with Poisson distribution, and mortality will be analysed using Cox regression. When 72 access-related serious adverse events have taken place, an interim safety analysis has sufficient power to show non-inferiority with regards to access-related serious adverse events at a margin of 0.5 events per patient-year with a power of 90%. When non-inferiority has not been reached, further analysis for superiority of either study group will be done. Statistically significant differences between study groups will be used as a guideline to issue recommendations by the DSMB. Reasons to disregard a statistically significant difference between study groups by the DSMB will be recorded. More weight will be given to access-related serious adverse events than to vascular access thrombosis. When the analysis shows neither non-inferiority nor superiority, additional interim safety analyses with more follow-up time may be done at the discretion of the DSMB.

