2.3. Sample size

Sample sizes were estimated for the number of interventions required for each patient-year of dialysis treatment (i.e. the primary outcome), which will be analysed using a general linear model with Poisson distribution and time as off-set variable. In the FLOW project, we aim to detect a difference in the intervention rate of 0.25 per year between study groups in a superiority analysis. This difference is associated with an economically relevant effect of saving approximately 1 million euros per year at a 75% de-implementation rate. The minimal clinically relevant difference in the intervention rate remains to be defined for this core outcome measure, but will likely be greater than 0.25 per year. In the Netherlands, the access-related intervention rate in hemodialysis patients with arteriovenous fistulas and grafts was 1.56 and 3.30 per year, respectively, in a retrospective observation cohort study in 10 dialysis units. As the distribution between fistulas and grafts is approximately 8:1, these figures amount to an average of 1.77 interventions per patient-year in the Netherlands. Since the study includes young hemodialysis patients waiting for kidney transplantation and old hemodialysis patients with limited life expectancy, 20% of participants are expected to leave the study per year before completing the follow-up period. A total follow-up time of 828 patient-years (414 patient-years in each treatment arm) achieves 80% power to detect a 0.25 decrease in the number of interventions per patient-year between the study groups using a two-sided, large-samples z-test of the Poisson event-rate difference at a significance level of 0.05. With a standard follow-up of 2 years and a drop-out rate of 20% per year, this would require a sample size of 518 patients. Implementing a variable follow-up time of a minimum of 2 years and a maximum of 3 years is expected to result in 162 additional patient-years. This corresponds to 101 patients with 2-years of follow-up and a drop-out rate of 20% per year, and therefore leads to a new sample size estimation of 417 patients. An interim analysis for safety requires a sample size of 144 patients (72 in each treatment arm) contributing 1 year of follow-up with an expected event rate of 0.5 events per patient-year to show non-inferiority with regards to access-related serious adverse events at a margin of 0.5 events per patient-year with a power of 90%.

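### SAP 2.5.3 prescribes the test of difference in access-related SAEs only when non-inferiority is not reached, and leaves a result that is non-inferior but significantly worse without a rule

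*SAP*

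**What the plan says.** SAP section 2.5.1 has the DSMB carry out an "interim safety analysis when the trial participants have contributed 72 access-related serious adverse events", expected at 144 patient-years. Section 2.3 gives the basis: the analysis "requires a sample size of 144 patients (72 in each treatment arm) contributing 1 year of follow-up", and the SAE rate it assumes is 0.5 per patient-year.

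Section 2.5.3 then sets out a sequence for access-related SAEs:

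1. Non-inferiority is tested against a margin of 0.5 events per patient-year, with a stated power of 90%.
2. The test of difference comes next, under a condition: "When non-inferiority has not been reached, further analysis for superiority of either study group will be done".
3. The criterion for the DSMB's advice is this: "Statistically significant differences between study groups will be used as a guideline to issue recommendations by the DSMB".
4. If neither non-inferiority nor superiority is shown, the DSMB may ask for further looks with more follow-up.

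The same section gives SAEs more weight than thrombosis. It states no non-inferiority step for thrombosis or mortality. Section 3.1 sets p<0.05 as the general significance level. No alpha or sidedness is given for the non-inferiority test.

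**The concern.** The DSMB's guideline is a statistically significant difference, but the step that would establish one for SAEs is written as conditional on failing non-inferiority. The margin is as large as the whole expected event rate (0.5 against 0.5 per patient-year). A confidence interval can therefore lie entirely above zero and entirely below the margin. For such a result the written sequence ends at non-inferiority: the test of difference is not called for, and neither are further looks, since those are tied to showing neither result.

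The trial asks whether surveillance can safely be abandoned, and SAEs are the safety endpoint given most weight. A rule that can pass a significant excess of serious events without comment leaves the DSMB to settle, with the data in hand, something that should be settled in advance.

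**Working it through.** **Inputs.** 72 events at the look and 144 patient-years expected (2.5.1). 72 patients per arm for 1 year and an expected rate of 0.5 per patient-year (2.3). Margin 0.5 per patient-year and power 90% (2.3, 2.5.3). Difference test at p<0.05 (3.1), taken as two-sided. Non-inferiority alpha is not stated, so one-sided 0.025 and 0.05 are both tried. Equal follow-up per arm is assumed.

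**Reproducing the stated figure.** On the log rate-ratio scale the margin is (0.5+0.5)/0.5 = 2. With one-sided alpha 0.05:

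- Patient-years per arm = (1.645+1.282)² × (1/0.5+1/0.5) / (ln 2)² = 71.3, i.e. 72.
- Power at 72 per arm = Φ(0.693/√(2/36) − 1.645) = 90.2%.

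The other versions tried do not match. An absolute difference with variance at equal rates needs 43 per arm (one-sided 0.025) or 35 (0.05). With variance at the margin it needs 64 or 52. The log scale at one-sided 0.025 needs 87.5. So the margin is worded as an absolute rate, while the 90% power fits a rate ratio of 2 at one-sided 0.05.

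**Overlap on the absolute margin, as worded.** Let x and y be the events in the worse and better arms, x+y = 72, and P the patient-years per arm. Then d = (x−y)/P and SE = √72/P = 8.485/P.

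- Significantly worse: x−y > 1.96 × 8.485 = 16.63. With an even difference this means at least 18, i.e. 45:27 or more extreme.
- Non-inferior at one-sided 0.025: x−y < 0.5P − 16.63.
- Non-inferior at one-sided 0.05: x−y < 0.5P − 13.96.

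At the planned P = 72 the non-inferiority limits are 36 − 16.63 = 19.37 and 36 − 13.96 = 22.04.

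| Split | d | Upper limit, 1.96 SE | Upper limit, 1.645 SE | Two-sided p | Both results? |
|---|---|---|---|---|---|
| 45:27 | 0.250 | 0.481 | 0.444 | 0.034 | yes, either alpha |
| 46:26 | 0.278 | 0.509 | 0.472 | 0.018 | only at one-sided 0.05 |
| 47:25 | 0.306 | 0.537 | 0.499 | 0.0095 | only at one-sided 0.05 |

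For 45:27 the rate ratio is 1.67, the lower limit of d is 0.019, and the exact binomial p is 0.044.

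**How often.** With 72 patient-years per arm and a rate of 0.5 in the surveillance arm, the chance of meeting both conditions is 2.8% if the true monitoring rate is 0.70 and 2.0% if it is 0.75 (one-sided 0.025). At one-sided 0.05 it is 9.6% and 8.6%. These true rates are assumptions.

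**Other event rates.** The look is triggered by an event count but the margin is an absolute rate, so the overlap depends on how long 72 events take. The pooled rates other than 0.5 are assumptions (one-sided 0.025):

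| Total patient-years | Pooled rate | Limit on x−y | Splits meeting both |
|---|---|---|---|
| 120 | 0.6 | 30 − 16.63 = 13.37 | none |
| 144 | 0.5 | 19.37 | 45:27 |
| 180 | 0.4 | 45 − 16.63 = 28.37 | 45:27 to 50:22 (ratio up to 2.3) |
| 240 | 0.3 | 60 − 16.63 = 43.37 | 45:27 to 57:15 (ratio up to 3.8) |

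At 120 total patient-years there is no overlap at one-sided 0.05 either (30 − 13.96 = 16.04, below 16.63).

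**Overlap on a rate-ratio margin of 2.** SE of the log ratio = √(1/x+1/y). At one-sided 0.05 the last non-inferior split is 41:31 (upper limit 1.956; 42:30 gives 2.074). At one-sided 0.025 it is 40:32 (upper limit 1.990). Significance again starts at 45:27, where the upper limits are 2.487 and 2.686. No split of 72 events meets both. Overlap would need about 4 × [(1.96+1.645)/0.693]² = 108 events at one-sided 0.05, or 128 at 0.025.

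**The case against.** A reader might infer that a significant SAE excess inside the margin would never come under the DSMB's guideline. The text does not support that. The guideline sentence, "Statistically significant differences between study groups will be used as a guideline to issue recommendations by the DSMB", carries no condition. The DSMB does the analysis itself, and section 3.1 calls for 95% confidence intervals, so an interval excluding zero would be visible. Thrombosis and mortality have no stated non-inferiority step, and section 5.5 counts thrombosis among the access-related events. The section is also guidance: the DSMB may set aside a significant difference with recorded reasons.

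A reader might also take any point estimate below 0.5 as passing. It is the upper confidence limit that must lie below 0.5. At the planned look, splits from 46:26 to 53:19 have an estimated difference under 0.5, yet at one-sided 0.025 they fail non-inferiority and are tested. At a true monitoring rate of 0.75, of the 47.8% chance of a significant excess, 45.9 percentage points fail non-inferiority first.

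On the rate-ratio scale that reproduces the plan's own power there is no overlap at all, and with equal follow-up patient-years cancel, so the widening at lower rates goes too. More extreme examples, such as 63:9 over 144 patient-years per arm, need an event rate half the stated one, which the SAP does not support.

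All of this stands and limits how often the gap matters. It does not remove the gap. The margin is stated in events per patient-year, and section 5.4.1 sends the interim to the section 5.2.2 model, which names an identity link while reporting a ratio. An unstated ratio scale cannot be relied on to close it.

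**Conclusion.** The concern holds in limited form. Section 2.5.3 prescribes no test of difference for access-related SAEs after non-inferiority is met, and is silent on a result that is both non-inferior and significantly worse. On the margin as worded that result is possible but uncommon at the planned look: one split of 72 events, or three with a one-sided 0.05 non-inferiority test. The range grows if the pooled SAE rate is below 0.5 per patient-year and is empty at 120 total patient-years or fewer.

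This rests on the absolute reading of the margin, equal follow-up per arm, the Wald approximation and a two-sided 0.05 difference test. It is a flaw in a stated safety rule that is worth correcting, short of a critical one. The primary analysis and the final safety analyses are not affected.

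**What to change.** In section 2.5.3, replace the conditional step with a statement that the two-sided 95% CI and the test of difference in access-related SAE rates are always produced and given to the DSMB, whatever the non-inferiority result. Add that meeting non-inferiority does not close the safety question when the difference is statistically significant against one arm. Carry the same wording into the DSMB's instructions. Stating the scale and alpha of the non-inferiority test in the same place would settle which overlap calculation applies.

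The cost is a sentence or two and one more p-value at a look that section 2.5.2 restricts to safety, with no early stopping for efficacy. No extra patients or data are needed. The SAP does not say whether the interim look has already taken place. If it has, the change can apply only to any further looks.

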2.6. Timing of final analysis

All results will be analyzed at the end of the study. Patients will be followed up for a minimum of 2 years and a maximum of 3 years (follow up will end for all participants when the last included patient has reached a 2 year follow-up period).

2.7. Timing of outcome assessments

Physical examination of the vascular access will be done at each dialysis session. Volume measurements by ultrasound dilution will be done every month. Duplex ultrasound examination of the vascular access will take place in case of flow dysfunction, and interventions for flow dysfunction are part of standard clinical care for hemodialysis patients. Subjects enrolled in the trial will be asked to fill out questionnaires (SF-VAQ, EQ-5D-5L, MCQ and PCQ) at baseline and every 3 months until 24 months of follow up.

3. Statistical Principles

3.1. General principles

Descriptive analyses will be reported using summary tables and figures. Continuous variables will be summarized with counts, means, standard deviations, medians, confidence intervals, minimums, and maximums where appropriate. Categorical variables will be reported by counts and percentages. Formal inferential statistical analyses techniques will be discussed in subsequent sections of this SAP. P-values <0.05 are considered statistically significant, unless otherwise stated in the SAP. 95% confidence intervals around estimates will be reported, unless otherwise stated in the SAP. Analyses and tabulations will be performed using R. All reported output will undergo a senior level statistical review to ensure valid methods were used, and that all data manipulations and calculations are correct and consistent with the SAP. Upon completion of the analysis, the analyses code will be collected and filed. Missing or invalid data will be treated as missing data (Section 5.3), unless otherwise stated.

3.2. Adherence and protocol deviations

3.2.1. Definition of adherence

When there is a clinical problem suggesting a vascular access stenosis or access flow is below 500mL/min (the latter only in the control group) there is an indication for intervention according the study protocol.

Non-adherence to the protocol may occur when patients are referred for correction of presumed vascular access stenosis based on parameters outside the study design (e.g. dynamic venous pressure).

3.2.2. Description of presenting adherence

In theory all interventions are done because of clinical problems or an access flow $< 500\text{mL/min}$ in the control group. Only interventions done for other reasons or cases where an intervention was not performed when necessary will be mentioned in the discussion.

3.2.3. Definition of protocol deviations

Not all possible protocol deviations are described in advance of the study. We focus on the protocol violations with regard to the primary endpoint and actively monitor those during the study period. For example, an intervention should be done when there are signs of vascular access stenosis present. On the other hand, no interventions are needed when there is no clinical problem or when based on other parameters outside the study design.

3.2.4. Description of which protocol deviations will be summarized

All protocol deviations are listed during the follow up. The protocol deviations that possibly influenced the final outcome will be mentioned in the discussion.

4. Trial Population

4.1. Screening data

All hemodialysis patients will be screened. Hemodialysis patients at the study sites who are not included in the clinical trial are registered in a screening log to determine the generalizability of the study population.

4.2. Eligibility

The study population are patients with end-stage renal disease who are treated with hemodialysis using arteriovenous vascular access.

4.2.1. Inclusion criteria

In order to be eligible to participate in this study, a subject must meet all of the following criteria:

1. Adult patients aged 18 years or older
2. End-stage renal disease with unlikely recovery of kidney function according to the attending nephrologist
3. Arteriovenous fistula or arteriovenous graft as hemodialysis vascular access that fulfills both of the following criteria at the time of trial enrolment:
 - a. Maturation: access flow volume of at least 500mL/min; and
 - b. Functional: the vascular access was cannulated with 2 needles and achieved the prescribed access circuit flow in at least 6 dialysis sessions over the past 30 days. Patients who have single needle hemodialysis for reasons other than vascular access dysfunction (e.g. for nocturnal hemodialysis) but who can be cannulated with 2 needles for flow measurements and fulfil the other requirements for a functional vascular access can be enrolled as well.
4. Planning to remain in one of the participating dialysis centers for at least 1 year

4.2.2. Exclusion criteria

A potential subject who meets any of the following criteria will be excluded from participation in this study:

1. Arteriovenous fistulas with multiple venous outflow paths upstream of the cannulation sites, that are not suitable for flow volume measurements using ultrasound dilution (e.g. Gracz fistulas and Ellipsys of WavelingQ endovascular fistulas)
2. Home hemodialysis
3. Thrombosis of the current vascular access in the past year
4. Planned access-related intervention
5. Living donor kidney transplantation, switch to peritoneal dialysis, or switch to home hemodialysis planned within 6 months
6. Life expectancy of less than 6 months, in the opinion of the attending nephrologist
7. Unable to provide informed consent.

4.3. Recruitment

Recruitment information will be presented using a flow diagram according the CONSORT statement for interventional studies. The recruitment and informed consent procedures are described in the main protocol section 11.2. The flow diagram will contain information on numbers of patients included in the study and screen failures. Reasons for nonparticipation are provided for each stage.

4.4. Withdrawal/follow up

4.4.1. Level of withdrawal

Subjects can leave the study at any time for any reason if they wish to do so without any consequences. The investigator can decide to withdraw a subject from the study for urgent medical reasons.

4.4.2. Timing of withdrawal

Patients who decided to leave the study or who have been withdrawn from the study for medical reasons will not be replaced. Data collected for the study will be used until the patient has withdrawn from the study. Patients who discontinue hemodialysis treatment after kidney transplantation, peritoneal dialysis, recovery of renal function, or refusal of further hemodialysis will be censored from the trial. Patients who decided to leave the study or who have been withdrawn from the study for medical reasons will receive standard medical care.

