2.1. Trial design

It is a double-blind, multicenter randomized controlled trial with a superiority framework and a 1:1 individual participant treatment allocation ratio over two study arms. In the intervention group, only symptomatic vascular access stenosis detected by clinical monitoring are treated, whereas in the comparison group asymptomatic stenosis detected by surveillance are treated as well (current standard of care in the Netherlands). Prevalent hemodialysis patients with a functional arteriovenous vascular access are eligible to participate in the trial. Patients will be followed up for a minimum of 2 years and a maximum of 3 years (follow up will end for all participants when the last included patient has reached a 2 year follow-up period) and will be censored when their mode of renal replacement therapy is changed to kidney transplantation, peritoneal dialysis, or conservative treatment.

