5.1.2. Secondary outcomes

1. Access-related complications per patient-year

Separate analyses will be performed on access-related complications graded as Clavien-Dindo grade 2 or higher and on access-related complications graded as Clavien-Dindo grade 4 or 5. The outcome will be defined as the number of access-related complications per patient-year.

- Access-related complications of Clavien-Dindo grade 2 or higher will be registered (30). Grade 2 complications require pharmacological treatment including catheter thrombolysis, antibiotics and blood transfusions. Complications that require no pharmaceutical or interventional treatment (grade 1) are not considered relevant for this clinical trial.
- Access-related complication of Clavien-Dindo grade 4 or 5 (i.e. admission to intensive care unit or death) are considered serious adverse events. As an exception, postoperative intensive care unit admission for vasopressor therapy to prevent early vascular access thrombosis is not considered a serious adverse event or complication.

2. Vascular access thrombosis rate

Vascular access thromboses will be defined as the absence of thrill and bruit, with confirmation of no flow by duplex ultrasound if deemed necessary by the treating physician at the study site. The outcome will be defined as the number of vascular access thrombosis events per person-year.

3. All-cause mortality

All-cause mortality will be defined as death by any cause during follow-up.

4. Access-related health care costs from randomization until the end of follow-up

Healthcare costs will be derived from hospital registration systems at the individual participant level. Costs to patients and families will be measured at the individual participants level using a study-specific adaptation of the Medical Consumption Questionnaire and Productivity Cost Questionnaire

developed by the institute for Medical Technology Assessment. Patients will be asked to report the data from their cost questionnaire every 3 months during the follow-up period.

5. Patient-reported outcome measures

For the patient-reported outcome measures the Short-form Vascular Access Questionnaire (SF-VAQ) and the Dutch version of the 5-level EuroQol 5-dimensional questionnaire (EQ-5D-5L) will be used.

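### One censoring rule serves every outcome, so deaths after a patient stops hemodialysis are left out of all-cause mortality

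*SAP*

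**What the plan says.** Two sections of the SAP set the censoring rule, and both state it for the trial as a whole. In section 2.1 patients are "censored when their mode of renal replacement therapy is changed to kidney transplantation, peritoneal dialysis, or conservative treatment". Section 4.4.2 lists the reasons for stopping hemodialysis and closes with "recovery of renal function, or refusal of further hemodialysis will be censored from the trial".

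The mortality outcome is item 3 of section 5.1.2: "All-cause mortality will be defined as death by any cause during follow-up". Section 2.5.2 names the interim safety measures as "vascular access thrombosis rate, access-related serious adverse event rate and mortality", and section 2.5.3 adds that "mortality will be analysed using Cox regression". At the final analysis, Table 4A reports death by arm over patient-years.

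Table 2O (End of study) has a row for conservative care under stopped hemodialysis, and a separate row for death.

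**The concern.** Ending observation when dialysis stops suits the primary outcome, which is a rate per patient-year of hemodialysis: once dialysis has ended there is no time at risk. All-cause mortality is different. Inclusion criterion 2 (section 4.2.1) restricts entry to patients whose kidney function is unlikely to recover, and section 2.3 expects some older participants with a short life expectancy. If such a patient stops dialysis and receives no transplant or peritoneal dialysis, death is the expected next event. A rule that censors on that day removes the patient just before the outcome.

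Cox regression needs censoring that carries no information about the hazard. Here it carries a great deal. The trial asks whether surveillance can be abandoned safely (section 1.2), and mortality is one of the quantities shown to the DSMB, so the loss falls on a named safety outcome.

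**Working it through.** No figure in the SAP decides this point. The check is to set the passages side by side and follow one patient through them.

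1. A randomized patient refuses further hemodialysis, or moves to conservative care, on day *t*.
2. Sections 2.1 and 4.4.2 censor the patient on day *t*. The wording of 4.4.2 covers the trial, not a particular outcome.
3. The patient dies some time after *t*. Section 5.1.2 item 3 requires the death to fall within follow-up, and for this patient follow-up ended at *t*.
4. The Cox analysis in 2.5.3 therefore has a censored observation, and the death row of Table 4A has no event. Table 2O would most naturally record an exit for conservative care.
5. No other section restores the death. Sections 2.4, 4.4.3 and 5.3 say only that no loss to follow-up is expected, because participants are seen at dialysis. That reason lapses once dialysis stops. The SAP states no collection of vital status after censoring, no competing-event method and no sensitivity analysis for mortality.

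**How many patients could be affected (illustration only).** The nearest figure in the SAP is "20% of participants are expected to leave the study per year before completing the follow-up period" (section 2.3), with 417 patients.

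- Exits over two years: 417 × (1 − 0.8²) = 417 × 0.36 ≈ 150.
- The SAP does not split these by reason. If 5%, 10%, 20% or 30% were dialysis cessation (assumed), about 8, 15, 30 or 45 patients would be censored at that point.
- These are patients, not deaths. They bound the deaths missed among such two-year exits; follow-up beyond two years would add some.

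**What it could do to a comparison (illustration only).** Let *s* be the share of deaths in the reference arm that follow cessation, and *k* the ratio of such deaths in the other arm to those in the reference arm, with all other deaths equal. The true mortality ratio is then (1 − *s*) + *s* × *k*, while the censored analysis targets about 1.0.

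| *s* (assumed) | *k* (assumed) | True ratio | Censored analysis |
|---|---|---|---|
| 0.1 to 0.3 | 1.0 | 1.00 | 1.0 |
| 0.1 | 1.5 | 0.90 + 0.15 = 1.05 | 1.0 |
| 0.2 | 2.0 | 0.80 + 0.40 = 1.20 | 1.0 |
| 0.3 | 2.0 | 0.70 + 0.60 = 1.30 | 1.0 |

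The first row matters as much as the others: if cessation is equally common in both arms, the ratio is not distorted and only the level of mortality is too low. Either arm may be the reference, so the table says nothing about direction.

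**The case against.** The best case for the plan has four parts.

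**The wording may be loose rather than wrong.** Sections 2.1 and 2.6 also say that follow-up closes for everyone at a common date, so a death after cessation could be read as still within follow-up. Table 2O gives no precedence rule when death follows conservative care. The protocol, which is not shown, may provide for vital status. This stands as a reason for clear wording, but it does not rescue the text: 4.4.2 removes these patients from the trial, and nothing in the SAP brings their deaths back.

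**The effect may be small.** At the interim, expected at 144 patient-years, assumed rates of 8 to 16 deaths per 100 patient-years give 12 to 23 deaths. If 10% to 30% of them follow cessation (assumed), about 1 to 7 are lost across both arms. The upper rate is itself a stretch, since 16 of the 20 exits per 100 patients per year would then be deaths, leaving little for transplantation. The interim is also triggered by access-related serious adverse events, not by mortality. All of this is fair.

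**The access signal is not lost.** A reader might infer that the rule hides the harm from a failed access. It does not. Abandonment is a safety endpoint (section 5.5) with its own row in Table 4A, and catheter placement and new access count in the primary outcome (section 5.1.1). What is lost is the later death.

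**No direction of bias is shown.** A reader might also infer that the hazard ratio is tilted towards one arm, for instance a false benefit of monitoring. That needs different cessation rates in the two arms, and the SAP gives no information on these. Table 2O, which shows exits for conservative care by arm, would at least reveal an imbalance.

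**Conclusion.** The point holds. As written, the SAP does not count deaths after conservative treatment or refusal of hemodialysis, and its Cox analysis of mortality treats strongly informative censoring as non-informative. The consequence that follows from the text is that mortality is understated in both arms, to the extent that patients stop dialysis and then die before the common end date.

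This rests on two premises: that the censoring sections mean what they say for every outcome, and that death commonly follows dialysis cessation in this population. The size cannot be computed. The counts and ratios above depend on assumed shares and should not be quoted as estimates. The primary outcome is untouched, so this is a correction that should be made to a secondary safety outcome, not a threat to the trial's main result.

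**What to change.** - **Sections 2.1, 4.4.2 and 5.1.2 item 3:** limit censoring at dialysis cessation to the intervention, thrombosis, patency and other access-related outcomes.
- **All-cause mortality, interim and final:** ascertain vital status from the medical file to the common end date for every randomized patient, unless consent is withdrawn, and count deaths after conservative care or refusal as events. Covering all exits avoids following the sicker leavers while dropping those who were transplanted. Censoring at transplantation or peritoneal dialysis can be kept as a sensitivity analysis.
- **Arm attribution:** state it in advance. The SAP provides for later randomizations (Table 2L, Figure 2E), and Table 2O groups patients by their allocation at the end of study. Choose a rule consistent with that handling and add an analysis by initial randomization as a sensitivity analysis.
- **Table 2O:** add a row, by arm, for patients who moved to conservative care and then died.

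The cost is SAP wording, one table row and a records check for patients who have left the dialysis unit; no extra visits are needed. The records may not capture every later death, so the number with unknown vital status should be reported by arm. The reported mortality can be expected to rise in both arms.
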